11.4 Pharmacokinetic, Pharmacodynamic, Pharmacogenomic, and Other Biomarker Assessments

11.4.1 Pharmacokinetic Assessments

Plasma concentrations of FLX475 will be measured.

Blood samples for PK analysis will be collected as specified in the Schedule of Procedures/Assessments in [Table 6](#). In addition, blood samples may be drawn at the investigator's discretion, e.g., during the occurrence of a clinically significant AE potentially related to study treatment. Study sites must have appropriately trained staff and adequate equipment for procuring and processing specimens. Instructions for the collection, handling, and shipping procedures of PK samples will be provided in the laboratory manual.

See [Sections 12.1.2.2](#) and [12.1.7](#) for more details.

11.4.2 Pharmacodynamic, Pharmacogenomic, and Other Biomarker Assessments

Blood samples for analysis of whole blood or serum biomarkers will be collected as specified in [Appendix 6](#) and in the Schedule of Procedures/Assessments in [Table 6](#). Blood samples

may also be drawn at the investigator's discretion, e.g., during the occurrence of a clinically significant AE potentially related to study treatment.

Biomarker discovery and/or validation may be performed to identify blood or tumor biomarkers that may be useful to predict subject response to study treatment, evaluation of response-related and/or safety-related outcomes as well as for potential use in diagnostic development (if optional subject consent for sample banking is provided). Blood samples may undergo enzyme-linked immunosorbent assay-based analyses or multiplex bead-based immunoassay, and/or DNA/RNA analysis, but not limited to, in an effort to identify biomarkers. In addition, biomarkers identified in other clinical studies of study treatment may also be assessed in samples collected from subjects enrolled in this study. The decision to perform biomarker analysis may be based on the clinical outcome of this study and/or the signals observed in other clinical studies or other information available at that time.

Pharmacodynamic and Pharmacokinetic/Pharmacodynamic:

Immunophenotyping: Blood samples will be obtained for T/B/NK and T cell panels as specified in the Schedule of Procedures/Assessments in [Table 6](#).

Plasma concentration data for FLX475 from the study may be used to explore PK/pharmacodynamic relationships for effects of FLX475 in combination with ipilimumab on objective response rate (ORR), other efficacy-related parameters including progression-free survival (PFS) and OS, and AEs/dose reduction. Exploratory/graphical analyses will be conducted for PK/pharmacodynamic evaluations and, if possible, may be followed by model-based analyses.

Any pharmacodynamic analyses may be detailed in a separate analysis plan and the results provided in a stand-alone report.

Pharmacogenetic/Pharmacogenomic (PG) Assessments

All subjects enrolled in the study will provide a core biopsy (minimum of 3 cores) or excisional (or skin punch) biopsy of a tumor lesion prior to starting treatment and on Cycle 2 Day 8 (± 7 days) (minimum of 3 cores). Optionally, additional biopsies may be obtained at clinically significant time points (e.g., early disease response or upon PD) with subject consent.

Tissue from the biopsy of tumor lesions will be collected for potential assessment of mutations and other genetic alterations or genes or proteins that may be important in the development and progression of cancer as well as in response to study treatment for potential use in diagnostic development. Genetic alterations in selected molecular targets may be explored based on their potential involvement in tumor biology. Immune cell profiling and molecular targets and factors involved in immune checkpoint axis, such as PD-1 or PD-L1 levels, markers of $T_{reg}/Th1/Th2$ phenotype, and inflammatory status, may also be explored. Appropriate technology/methodologies will be used based on the amount of tumor tissue available.

A blood sample may be collected for potential pharmacogenomic analysis from all enrolled subjects (in accordance with regional or local laws). Variation in FLX475 exposure or the occurrence of AEs observed in the study population may be evaluated by correlating single-nucleotide polymorphisms with PK, safety, or pharmacodynamic data.

Any data obtained will be used for research purposes to assist in developing safer and more effective treatments and will not be used to change the diagnosis of the subject or alter the therapy of the subject. The DNA will not be used to determine or predict risks for diseases that an individual subject does not currently have. Any sample or derivatives (DNA, RNA, and protein) may be stored for up to 15 years (if optional subject consent for sample banking is provided) to assist in any research scientific questions related to study treatment, cancer and/or for potential diagnostic development.

Instructions for the processing, storage, and shipping of samples will be provided in the Laboratory Manual.

11.5 Safety Assessments

Safety assessments will consist of monitoring and recording of all AEs and SAEs using CTCAE v5.0 ([Appendix 1](#)), regular laboratory evaluation for hematology, blood chemistry, and urine values; regular performance of physical examinations and vital sign measurements; and periodic ECGs.

11.5.1 Adverse Events and Events of Clinical Interest

An AE is any untoward medical occurrence in a patient or clinical investigation subject administered an investigational product. For this study, the study treatments are FLX475 and ipilimumab. An AE does not necessarily have a causal relationship with the medicinal product. Progression of the cancer under study is not considered an AE.

Adverse events, SAEs, and other reportable safety events must be reported to the investigator by the subject (or, when appropriate, by a caregiver, surrogate, or the subject's legally authorized representative).

The criteria for identifying AEs in this study are:

- Any unfavorable and unintended sign (including an abnormal laboratory finding), symptom, or disease temporally associated with the use of an investigational product, whether or not considered related to the investigational product (Note: Every sign or symptom should not be listed as a separate AE if the applicable disease [diagnosis] is being reported as an AE).
- Any new disease or exacerbation of an existing disease. However, worsening of the primary disease should be captured under efficacy assessments as disease progression rather than as an AE.
- Any deterioration in non-protocol-required measurements of a laboratory value or other clinical test (e.g., ECG or radiograph) that results in symptoms, a change in treatment, or discontinuation of study treatment.

- Recurrence of an intermittent medical condition (e.g., headache) not present pretreatment (Baseline).
- An abnormal laboratory test result should be considered an AE if the identified laboratory abnormality leads to any type of intervention, withdrawal of study treatment, or withholding of study treatment, whether prescribed in the protocol or not.

The investigator, who is a qualified physician, and any designees are responsible for detecting, assessing, documenting, and reporting events that meet the definition of an AE or SAE, as well as other reportable safety events (e.g., pregnancy). Investigators remain responsible for following up AEs, SAEs, and other reportable safety events for outcome.

All AEs observed during the study will be reported on the appropriate eCRF.

All AEs, SAEs, and other reportable safety events, regardless of relationship to study treatment or procedure, that occur after the consent form is signed but before treatment has started, must be reported by the investigator if the event caused the subject to be excluded from the study, or is the result of a protocol-specified intervention, including but not limited to, washout or discontinuation of usual therapy, diet, or a procedure.

Abnormal laboratory values should not be listed as separate AEs if they are considered to be part of the clinical syndrome that is being reported as an AE. It is the responsibility of the investigator to review all laboratory findings in all subjects and determine if they constitute an AE. Medical and scientific judgment should be exercised in deciding whether an isolated laboratory abnormality should be classified as an AE. Any laboratory abnormality considered to constitute an AE should be reported on the Adverse Event eCRF.

Abnormal ECG (QTc) results, if not otherwise considered part of a clinical symptom that is being reported as an AE, should be considered an AE if the QTcF interval is ≥ 450 ms and there is an increase of more than 60 ms from baseline. Any ECG abnormality that the investigator considers as an AE should be reported as such.

All AEs or events of clinical interest (ECIs) that occur from the start of treatment through 30 days following cessation of study treatment must be reported on the eCRF by the investigator. See [Section 11.5.2](#) for further discussion of SAEs and ECIs.

All AEs present at time of cessation of study treatment must be followed for 90 days after the subject's final dose (or 30 days after final dose if the subject initiates new anticancer therapy), or until resolution, whichever comes first. All SAEs must be followed to resolution or, if resolution is unlikely, to stabilization.

Every effort must be made by the investigator to categorize each AE according to its severity and its relationship to the study treatment.

Assessing Severity of Adverse Events

Adverse events will be graded on a 5-point scale according to CTCAE v5.0 ([Appendix 1](#)). Investigators will report CTCAE grades for all AEs (for both increasing and decreasing severity).

Assessing Relationship to Study Treatment

Items to be considered when assessing the relationship of an AE to the study treatment are:

- Temporal relationship of the onset of the event to the initiation of the study treatment
- The course of the event, especially the effect of discontinuation of study treatment or reintroduction of study treatment, as applicable
- Whether the event is known to be associated with the study treatment or with other similar treatments
- The presence of risk factors in the study subject known to increase the occurrence of the event
- The presence of non-study, treatment-related factors that are known to be associated with the occurrence of the event

Classification of Causality

The relationship of each AE to the study treatment will be recorded on the eCRF in response to the following question:

Is there a reasonable possibility that the study treatment caused the AE?

Not Related A causal relationship between the study treatment and the AE is not a reasonable possibility.

Possibly Related Has a chronological relationship with the time of study drug administration and/or represents a known reaction to study drug but probably the result of another factor; not clearly the result of an external factor.

Probably Related Has a chronological relationship with the time of study drug administration and/or represents a known reaction to study drug but possibly the result of another factor; not clearly the result of another factor, disappears or decreases after discontinuation of the study drug.

Definitely Related Has a chronological relationship with the time of study drug administration and/or represents a known reaction to study drug, not the

result of another factor, disappears or decreases after discontinuation of the study drug, and recurs on re-challenge (if restarted).

11.5.2 Serious Adverse Events, Events of Clinical Interest, and Events Associated with Special Situations

An SAE is defined as any untoward medical occurrence that at any dose:

- Results in death
- Is life-threatening (i.e., the subject was at immediate risk of death from the adverse event as it occurred; this does not include an event that, had it occurred in a more severe form or was allowed to continue, might have caused death)
- Requires inpatient hospitalization or prolongation of existing hospitalization
- Results in persistent or significant disability/incapacity
- Results in a congenital anomaly/birth defect (in the child of a subject who was exposed to the study treatment)

Other important medical events that may not be immediately life-threatening or result in death or hospitalization but, when based on appropriate medical judgment, may jeopardize the subject or may require intervention to prevent one of the outcomes in the definition of SAE listed above should also be considered SAEs. Medical and scientific judgment should be exercised in deciding whether expedited reporting is appropriate in such situations.

Events of clinical interest (ECIs) in this study, whether serious or not, include:

1. An overdose of FLX475 or ipilimumab, as defined in [Section 11.5.3, Overdose](#), that is not associated with clinical symptoms or abnormal laboratory results.
2. QTcF interval \geq 450 ms with a $>$ 60 ms increase from baseline (defined as average QTcF value from C1D1 pre-dose ECGs)

In addition to the above ECIs, events associated with special situations include pregnancy or exposure to study treatment through breastfeeding; AEs associated with study treatment overdose, misuse, abuse, or medication error. Events associated with special situations and ECIs are to be captured using the SAE procedures but are to be considered as SAEs only if they meet one of the above criteria. All AEs associated with special situations are to be reported on the eCRF whether or not they meet the criteria for SAEs. Any occurrences of pregnancies and exposure during breastfeeding must be reported by the investigator from the start of treatment through 120 days following cessation of study treatment, or 30 days following cessation of study treatment if the subject initiates new anticancer therapy, whichever is earlier.

Serious AEs must be reported for 90 days after the subject's final dose of study treatment, or for 30 days after the final dose of study treatment if the subject initiates new anticancer therapy, whichever is earlier. Additionally, any SAE brought to the attention of an investigator at any time outside the time periods specified above must be reported immediately to the Sponsor if the event is considered to be drug-related. All SAEs must be followed to resolution or, if resolution is unlikely, to stabilization.

The following hospitalizations are not considered to be SAEs because there is no "adverse event" (i.e., there is no untoward medical occurrence) associated with the hospitalization:

- Hospitalizations for respite care
- Planned hospitalizations required by the protocol
- Hospitalization planned before informed consent (where the condition requiring the hospitalization has not changed after study treatment administration)
- Hospitalization for administration of study treatment or insertion of access for administration of study treatment
- Hospitalization for routine maintenance of a device (e.g., battery replacement) that was in place before study entry

If possible, blood sample(s) for the measurement of FLX475 plasma concentration should be drawn at the first report of an SAE or a severe unexpected AE and at its resolution.

11.5.3 *Overdose*

For this study, an overdose of FLX475 will be defined as any dose \geq 2 times the indicated dose. An overdose of ipilimumab will be defined as any dose of \geq 3 times the planned dose. No specific information is available on the treatment of an overdose of FLX475 or ipilimumab. In the event of an overdose, the subject should be observed closely for signs of toxicity. Appropriate supportive treatment should be provided if clinically indicated.

11.5.4 *Pregnancy, Contraception, and Breastfeeding*

FLX475 and ipilimumab may have adverse effects on a fetus in utero. Furthermore, it is not known if FLX475 or ipilimumab has transient adverse effects on the composition of sperm.

Subjects should be informed that taking the study drug(s) may involve unknown risks to the unborn baby if pregnancy were to occur during the study. In order to participate in the study, subjects of childbearing potential must adhere to the contraception requirement (from the start of study treatment [or 14 days prior to the initiation of study treatment for oral contraception] throughout the study period up to 120 days after the final dose of study treatment). If there is any question that a subject of childbearing potential will not reliably comply with the requirements for contraception, that subject should not be entered into the study.

If a female subject inadvertently becomes pregnant while receiving treatment with FLX475, ipilimumab or both, she must immediately discontinue study treatment. If a female partner of a male subject inadvertently becomes pregnant while the subject is receiving treatment with FLX475, ipilimumab, or both, the investigator must be informed immediately. The investigator will contact the subject at least monthly and document the status of the mother and pregnancy until the pregnancy has been completed or terminated (spontaneously or through induced abortion). See [Section 11.7.2](#) for reporting requirement.

It is unknown whether FLX475 or ipilimumab is excreted in human milk. Since many drugs are excreted in human milk, and because of the potential for serious adverse reactions of drugs in the nursing infant, females who are breastfeeding are not eligible for enrollment in this study.

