cycles will be counted continuously regardless of dose interruptions (i.e. all study visits are anchored to Cycle 1 Day 1). Subjects will undergo safety and efficacy assessments as defined in the Schedule of Procedures/Assessments ([Table 6](#)). Subjects will continue to receive study treatment for a maximum of 2 years (35 cycles) or until subject withdrawal from the study, confirmed progression of cancer, intolerable study treatment-related toxicity despite appropriate dose modification and supportive treatment, the development of intercurrent illness that precludes continued study treatment, pregnancy or breastfeeding, substantial noncompliance with study procedures, loss to follow-up, or study termination by the Sponsor, whichever occurs first. Treatment beyond 35 cycles may be considered only if it is felt to be in the best interests of the subject by the investigator and upon Sponsor agreement (if feasible).

- Subjects who discontinue ipilimumab prior to receiving the planned four doses due to toxicity may continue treatment with FLX475 alone.

For subjects who have radiological disease progression (PD) by Response Evaluation Criteria in Solid Tumors (RECIST) 1.1 as determined by the investigator, the investigator will decide in consultation with the Sponsor's medical monitor whether the subject can continue to receive study treatment until repeat, confirmatory imaging is obtained using modified RECIST for immunotherapies (iRECIST) for subject management (see [Appendix 5](#) for details). The investigator's decision is based on the subject's overall clinical condition.

8.2.3 *Follow-Up Phase*

Unless they withdraw consent or are lost to follow-up, subjects who discontinue study treatment will be followed for acquisition of safety information for 90 days after the final dose of study treatment (or 30 days following cessation of study treatment if the subject initiates new anticancer therapy, whichever occurs first). Subjects will also be followed for long-term collection of information regarding further therapies for cancer and overall survival (OS).

If a subject discontinues study treatment and does not consent to continued follow-up, the investigator must not access confidential records that require the subject's consent. However, an investigator may consult public records to establish survival status, as well as for OS (until death or loss to follow-up).

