10.5.2 Dose Modification for Ipilimumab

Adverse events associated with ipilimumab exposure may represent an immunologic etiology and may affect more than one body system simultaneously. These immune-related AEs (irAEs) may occur shortly after the first dose or several months after the final dose of ipilimumab. Therefore, early recognition and initiation of treatment is critical to reduce complications. Based on existing clinical study data, most irAEs are reversible and can be managed with interruptions of ipilimumab, administration of corticosteroids, and/or other supportive care. Suspected irAEs should be adequately evaluated to confirm etiology or exclude other causes. Additional procedures or tests such as bronchoscopy, endoscopy, skin biopsy may be included as part of the evaluation. Based on the severity of irAEs, ipilimumab should be withheld or permanently discontinued, and corticosteroids administered. Ipilimumab may cause severe or life-threatening infusion-reactions including severe hypersensitivity or anaphylaxis. Signs and symptoms usually develop during or shortly after drug infusion and generally resolve completely within 24 hours of completion of infusion. Note that modification of dosing of ipilimumab (e.g. withholding or discontinuation) due to

potential/likely ipilimumab toxicity (e.g. irAE) does not require similar modification of FLX475 dosing unless there is evidence of concurrent FLX475-related toxicity.

Thorough dose modification and toxicity management guidelines for irAEs associated with immunotherapies including ipilimumab have been published and should be followed ([Brahmer, et al., 2018](#)). Criteria for dose delay, modification, or discontinuation of ipilimumab are described below. Additional guidance regarding dose modification for ipilimumab can be found in Section 2.3 of the approved label ([Yervoy® Package Insert](#)).

[Table 3](#) shows treatment guidelines, including premedications, for subjects who experience an infusion reaction associated with the administration of ipilimumab. Examples of some of the most common irAEs are provided in [Table 4](#).

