12.1.8.2 Adverse Events

Adverse events will be graded using CTCAE v5.0. The AE verbatim descriptions (investigator terms from the eCRF) will be classified into standardized medical terminology using the Medical Dictionary for Regulatory Activities (MedDRA). Adverse events will be coded to the MedDRA lower level term closest to the verbatim term. The linked MedDRA preferred term (PT) and primary system organ class (SOC) are also captured in the database.

A TEAE is defined as an AE that starts or worsens in severity any time after the first dose of study treatment until 30 days after the last dose of study treatment. Only those AEs that are treatment-emergent will be included in summary tables. All AEs, treatment-emergent or otherwise, will be presented in subject data listings.

The TEAEs will be summarized. The incidence of TEAEs will be reported as the number (percentage) of subjects with TEAEs by SOC and PT. A subject will be counted only once within an SOC and PT, even if the subject experienced more than 1 TEAE within a specific SOC and PT. The number (percentage) of subjects with TEAEs will also be summarized by maximum severity (highest CTCAE grade).

The number (percentage) of subjects with treatment-related TEAEs will be summarized by SOC and PT. Treatment-related TEAEs include TEAEs that were considered by the investigator to be possibly or probably related to study treatment or TEAEs with a missing causality. The number (percentage) of subjects with treatment-related TEAEs will also be summarized by maximum severity (by highest CTCAE grade).

The proportion of subjects who discontinue treatment due to toxicity will be summarized by frequency counts and percentages

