7.5.2 Adverse Events

All subjects will be assessed regularly for the potential occurrence of adverse events (AEs) from the date of informed consent to 90 days after the last dose of study treatment. The incidence of treatment-emergent adverse events (TEAEs) will be summarized and tabulated using Medical Dictionary for Regulatory Activities (MedDRA), by System Organ Class (SOC) and Preferred Term (PT). A TEAE is defined as an AE that first occurs or worsens in severity on or after the first dose of FLX475. All adverse events recorded in the eCRF will be presented in data listings.

The National Cancer Institute (NCI)/CTCAE v5.0 will be used to grade both clinical and laboratory AEs. A subject with several occurrences of the same AE will be counted once

and classified by the most severe occurrence. AEs with missing severity ratings will be classified as having unknown severity, but will be assigned Grade 3 severity for analysis and summarization.

The relationship of each AE to the study treatment will be classified as related or unrelated; an AE that is possibly, probably or definitely related to study treatment will be considered related. Any AE with an eCRF description of related will be considered related. A subject with several occurrences of the same AE will be counted once and classified as related if at least one of them is classified as related. An AE with a missing relationship to study treatment will be assumed to be related to study treatment for the purpose of analysis and summarization. Relationship of AEs to FLX475 and ipilimumab will be separately recorded and analyzed.

An overview of adverse events for the Safety Analysis Set will be provided, summarizing the incidence of the following:

- Any DLT;
- Any TEAEs; FLX475-related TEAEs; ipilimumab-related TEAEs;
- Any NCI/CTCAE Grade ≥ 3 TEAEs; FLX475-related NCI/CTCAE Grade ≥ 3 TEAEs; ipilimumab-related NCI/CTCAE Grade ≥ 3 TEAEs;
- Any serious TEAEs; FLX475-related serious TEAEs; ipilimumab-related serious TEAEs;
- Any discontinuation of study treatment due to TEAEs; discontinuation of FLX475 due to FLX475-related TEAEs; discontinuation of ipilimumab due to ipilimumab-related TEAEs;
- Any NCI/CTCAE Grade 5 TEAEs; FLX475-related NCI/CTCAE Grade 5 TEAEs; ipilimumab-related NCI/CTCAE Grade 5 TEAEs.

TEAE summaries by SOC and PT will be provided for the following:

- TEAEs (overall and FLX475 or ipilimumab related);
- Grade ≥ 3 TEAEs (overall and FLX475 or ipilimumab related);

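### The documents give two collection windows for new adverse events (30 and 90 days) and two TEAE definitions, so late non-serious immune toxicity may go unrecorded in subjects who stop both drugs early

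*Protocol*

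**What the plan says.** **Expected timing of harm.** Protocol 10.5.2 says that irAEs "may occur shortly after the first dose or several months after the final dose of ipilimumab".

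**Texts giving 30 days.**
- Protocol 11.5.1, on AEs and events of clinical interest: those "that occur from the start of treatment through 30 days following cessation of study treatment must be reported on the eCRF". SAP 6.4.2.1 carries the same sentence.
- Protocol 12.1.8.2 defines a TEAE as starting or worsening "any time after the first dose of study treatment until 30 days after the last dose of study treatment" and adds: "Only those AEs that are treatment-emergent will be included in summary tables".
- Protocol 10.10.1 records concomitant therapy to 30 days after the final dose. Protocol 10.10.4 extends this to 90 days only for SAEs and events of clinical interest.

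**Texts giving 90 days or no end.**
- Protocol 8.2.3: subjects who discontinue are "followed for acquisition of safety information for 90 days after the final dose of study treatment", or for 30 days after cessation if new anticancer therapy starts.
- Protocol Table 6, footnote s: follow-up for drug-related AEs and ongoing SAEs runs 90 days or until they resolve or stabilise, with the same shortening for new therapy.
- SAP 7.5.2: AEs are assessed from consent to 90 days after the last dose, and "A TEAE is defined as an AE that first occurs or worsens in severity on or after the first dose of FLX475". No end date is given.

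**Serious events.** Protocol 11.5.2 requires SAE reporting to 90 days, or 30 days if new anticancer therapy starts. SAEs considered drug-related are reportable at any time.

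**The concern.** Sites follow the eCRF rule. As written, that rule closes 30 days after study treatment stops, while the protocol itself expects some immune toxicity to appear later. A non-serious irAE in that interval can still be important: a Grade 3 event managed as an outpatient and not judged medically important is one example. Nothing else in the protocol brings such an event back in, because the events of clinical interest in 11.5.2 are only overdose and QTcF prolongation.

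Safety and tolerability is a primary objective. SAP 6.4.1.1, 7.4.1 and 7.7 drop the efficacy summaries, so safety is the only primary objective the SAP will report. Protocol 6.2 states that FLX475 is not expected to add materially to ipilimumab's immune toxicity and promises close monitoring for it. If sites read the conflicting windows differently, late events will be captured unevenly, and the tables will not show which rule was applied.

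**Working it through.** The plan states no figure to reproduce. The check compares the texts and then applies calendar arithmetic.

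**1. Do the 90-day texts require a new non-serious AE on the eCRF?**
- The 90-day sentence in protocol 11.5.1 reads "All AEs present at time of cessation of study treatment must be followed for 90 days after the subject's final dose". It covers events already present at cessation, not new ones.
- Protocol 8.2.3, Table 6 footnote s and SAP 7.5.2 speak of acquiring safety information, following and assessing. None states an eCRF rule for a new non-serious AE.
- Protocol 11.5.1 also says generally that AEs observed during the study go on the eCRF, which sits uneasily with its own 30-day limit.

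A site can therefore defend either reading. The explicit eCRF instruction is the 30-day one.

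**2. What is tabulated?** Under protocol 12.1.8.2, only events up to 30 days after the last dose. Under SAP 7.5.2, any event on the eCRF that starts or worsens on or after the first FLX475 dose. SAP 7.7 lists only the dropped efficacy summaries as a departure from the protocol, so the TEAE change is undeclared.

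**3. Calendar.** Inputs: 21-day cycles and up to four ipilimumab doses on Day 1 of Cycles 1 to 4 (protocol 8.1, 10.3); first scan at 9 weeks ± 7 days (11.3.1.1); study treatment means both drugs (11.5.1).
- Fourth ipilimumab dose: 1 + 3 × 21 = Day 64.
- First scan: 1 + 63 = Day 64 (range Day 57 to 71).
- Both drugs stopped on Day 64, 30-day rule: 64 + 30 = Day 94.
- Same subject, 90-day period: 64 + 90 = Day 154.
- Difference: 154 − 94 = 60 days.

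**4. Effect of continuing FLX475.** The clock starts when all study treatment ends, so days covered after the last ipilimumab dose = days of FLX475 after that dose + 30.

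| FLX475 days after last ipilimumab dose (Day 64) | Days covered by the 30-day rule |
|---|---|
| 0 | 30 |
| 21 | 51 |
| 60 | 90 |
| 126 | 156 |
| to end of 35 cycles (35 × 21 = Day 735) | 735 + 30 − 64 = 701 |

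The shortfall is confined to subjects who stop both drugs early.

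**5. Scale.** With 20 planned subjects, one subject whose only irAE is unrecorded changes the observed proportion by 1/20 = 5 percentage points. This shows sensitivity; it does not estimate how many would be missed.

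**The case against.** The strongest reply is that the documents already use 90 days in several places, so this is an inconsistency rather than a window that is too short. Much of that stands.

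- **Tabulation.** A reader of protocol 12.1.8.2 might infer that late irAEs are tabulated only to 30 days. SAP 7.5.2 does not support that: its TEAE definition has no upper limit, so a late event on the eCRF would be tabulated. It cannot tabulate an event that was never entered.
- **Serious events.** A reader might infer that late Grade 3 irAEs in general are lost. They are not. Hospitalised events are SAEs, other important medical events can qualify by judgment, and drug-related SAEs are reportable at any time. The gap is in non-serious events.
- **Worst case.** Stopping both drugs on Day 64 is close to the extreme. A clinically stable subject may continue treatment until a repeat scan 4 to 8 weeks after first progression. That puts the last treatment at 64 + 28 = Day 92 to 64 + 56 = Day 120, and the 30-day limit at Day 122 to 150, which is 58 to 86 days after a Day 64 ipilimumab dose.
- **Direction of bias.** A reader might infer that the irAE rate is biased by a known amount in favour of the statement in protocol 6.2. The study is single-arm, no irAE comparison is planned, and no onset distribution is given. Under-recording is a risk, not a demonstrated result.
- **Timing.** The SAP records early discontinuation of the study, so changing data collection now may achieve little.

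What survives is that the explicit eCRF rule is the shortest of the competing windows, and the protocol's own account of irAE timing extends beyond it.

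**Conclusion.** The concern holds as a conflict between windows, with a risk of under-recording as its consequence. Protocol 11.5.1, protocol 12.1.8.2 and SAP 6.4.2.1 give 30 days. Protocol 8.2.3, Table 6 footnote s and SAP 7.5.2 give 90 days for follow-up or assessment, and the SAP sets no end to the TEAE window. Under the 30-day rule, new non-serious irAEs starting on Day 31 to 90 after all study treatment stops need not be recorded, and neither need the medication given for them.

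The gap is at most 60 days relative to the 90-day period. It matters mainly for subjects who stop both drugs at about the same time and early. Those 60 of 90 days are a share of calendar time, not of events. Turning them into an irAE rate would need an onset distribution and a split between serious and non-serious irAEs, and the documents give neither. The conclusion assumes that sites apply the explicit eCRF instruction in preference to the general follow-up wording.

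**What to change.** Reconcile protocol 11.5.1, protocol 12.1.8.2 and SAP 6.4.2.1 with protocol 8.2.3, Table 6 footnote s, SAP 7.5.2 and the statement on irAE timing in protocol 10.5.2:

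1. In protocol 11.5.1 and SAP 6.4.2.1, require new immune-related AEs and new treatment-related AEs of Grade 3 or higher to be recorded on the eCRF through the existing 90-day safety follow-up. Extend protocol 10.10.1 and 10.10.4 so that concomitant treatment for these events is recorded too.
2. Leave the existing 30-day rule for subjects who start new anticancer therapy unchanged. Removing it would add follow-up that the plan does not have. SAP 7.5.2 does not mention this exception and should.
3. State one TEAE window, identically worded, in protocol 12.1.8.2 and SAP 7.5.2.
4. Add one table or listing of immune-related AEs from first dose to 90 days after last dose.
5. Record the TEAE definition change in SAP 7.7.

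If collection has already closed, items 3 to 5 can still be done, and the study report should say which recording rule the sites followed.

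The cost is wording in both documents, a few extra eCRF entries and one output. It adds no visits or tests and changes nothing in treatment. The reported irAE rate may rise slightly.
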